### 6.5.3. Laboratory Values

Clinical laboratory values will be evaluated for each laboratory parameter as appropriate.

Descriptive summary statistics (n, mean, standard deviation, median, Q1, Q3, minimum, and maximum for continuous variables; n [%] for categorical variables) for laboratory parameters and their changes from baseline will be summarized by visit and treatment group. Change from baseline will only be summarized for subjects with both baseline and postbaseline measurements. The percentage of abnormal values for laboratory parameters will be summarized by visit and treatment group.

Laboratory parameters that are graded in [NCI-CTCAE v5.0](#) will be summarized by shifts from baseline NCI-CTCAE grades to maximum postbaseline grades. In the summary of laboratory parameters by NCI-CTCAE grade, parameters with NCI-CTCAE grading in both high and low directions will be summarized separately.

Subject data listings of each parameter will be provided. Abnormal laboratory values will be flagged and identified as those outside (above or below) the normal range. Reference (normal) ranges for laboratory parameters will be provided.

### 6.5.4. Vital Signs

Descriptive statistics for vital sign parameters (systolic and diastolic blood pressure, pulse rate, respiratory rate, and body temperature), changes from baseline and the percentage of abnormal values will be summarized by visit and treatment group.

Subject data listings of each parameter will be provided. Abnormal values will be flagged and identified as those outside (above or below) the normal range. Reference (normal) ranges for vital signs parameters are defined as following:

- Respiratory rate: 10-22 bpm
- Temperature: 35.5-37.5 °C
- Systolic blood pressure: 90-140 mmHg
- Diastolic blood pressure: 40-90 mmHg
- Pulse rate: 60-100 bpm

### 6.5.5. Electrocardiograms (ECG)

Descriptive statistics for ECG parameters (heart rate and QTcF interval), changes from baseline and the percentage of abnormal values will be summarized by visit and treatment group.

ECG will be listed by treatment group, subject and visit. Abnormal values will be flagged and identified as those outside (above or below) the normal range. Reference (normal) ranges for ECG parameters are defined as following:

- Heart rate: 60-100 bpm
- QTcF interval:  $\leq 450$  msec

## 6.6. Pharmacokinetic Analyses

The following analysis plan provides the framework for the summarization of the PK data from study BGB-DXP604-101. The objective is to assess BGB-DXP604 and BGB-DXP593 PK and characterize PK parameters following a single IV dose. The PK analyses will include only subjects randomized to receive either BGB-DXP604 alone or in combination with BGB-DXP593 and with enough data to enable estimation of key parameters. Additional PK analyses (such as modeling and simulation using nonlinear mixed effects modelling) may be conducted if deemed necessary and will be described in a separate analysis plan.

### 6.6.1. Calculation of Serum Pharmacokinetic Parameters

Actual dose and blood draw times will be used to calculate the PK parameters. Parameters will be listed individually and summarized by treatment group using descriptive statistics.

The following serum PK parameters will be calculated for BGB-DXP604 and BGB-DXP593, as appropriate for the data collected. Other PK parameters may be calculated if supported by the data.

Calculation and presentation of PK parameters will be based on the [Work Instruction: Best Practice Guidance: Non-Compartmental Pharmacokinetic Data Analysis for Clinical Studies. Version 1.0, Document Number VV-QDOC-13140](#).

Parameter (Units)	Definition	Method of Determination
AUC 0-29 (µg·day/mL)	Area under the serum concentration versus time curve from 0 to Day 29	Calculated using the linear up/log down variant of the trapezoidal rule
AUC 0-8 (µg·day/mL)	Area under the serum concentration versus time curve from Day 1 to Day 8	Calculated using the linear up/log down variant of the trapezoidal rule
AUC 0-15 (µg·day/mL)	Area under the serum concentration versus time curve from Day 1 to Day 15	Calculated using the linear up/log down variant of the trapezoidal rule
AUC last (µg·day/mL)	AUC from time zero to time of last quantifiable concentration	Calculated using the linear up/log down variant of the trapezoidal rule
AUC inf (µg·day/mL)	AUC from zero to infinite time with extrapolation of the terminal phase	Calculated using the linear up/log down variant of the trapezoidal rule
C max (µg/mL)	Maximum observed drug concentration during a dosing interval	Reported value
t max (h)	Time to reach C max	Actual elapsed time for observed C max

$t_{1/2}$ (days)	half-life	$\ln(2)/\lambda_z$ , where $\lambda_z$ is the first-order rate constant of drug associated with the terminal portion of the curve
CL (L/h)	clearance	Calculated as Dose/AUC inf
V z (L)	volume of distribution during the terminal phase	Calculated as CL/ $\lambda_z$ , where $\lambda_z$ is the first-order rate constant of drug associated with the terminal portion of the curve

### 6.6.2. Reporting of Pharmacokinetic Concentrations for Descriptive Statistics

The PK analyst will appropriately flag and annotate treatment of any anomalous concentrations, exclusions and any special treatment for descriptive statistics and plots. The concentration and time data of BGB-DXP604 and BGB-DXP593 will be listed individually and summarized by treatment group using descriptive statistics.

The following conventions will be used for reporting descriptive statistics for concentration data.

- PK concentrations should be reported in listings at the same level of precision as that in the source data.
- If a concentration at a given time point is below the assay quantification limit (BLQ), the concentration shall be reported as the term “BLQ” with the lower limit of quantitation (LLOQ) defined in the footnotes. BLQ values shall be treated as zero for computation of descriptive statistics.
- If a concentration at a given time point is missing it shall be reported as a missing value. Missing values may be defined in a bioanalytical source as “NS” (no sample), “NR” (no result), “IS” (insufficient sample), etc. If missing data are not identified in the bioanalytical source (i.e., the record is missing), the reporting convention of “NS” shall be utilized.
- If the calculated mean concentration is BLQ, the mean value shall be reported in outputs (such as tables) as BLQ and SD and geometric CV% shall be reported as ND (not determined). Minimum, median, and maximum may be reported.

### 6.6.3. Plots of Pharmacokinetic concentrations

For BGB-DXP604 and BGB-DXP593, concentration versus time data will be plotted individually and summarized graphically using arithmetic mean ( $\pm$ SD) plots by treatment group, respectively. Arithmetic mean concentrations that are BLQ shall be set to zero for plotting on both linear scale and log-linear scale.

### 6.6.4. Reporting of PK Parameters for Descriptive Statistics

The PK analyst will appropriately flag and annotate treatment of any anomalous PK parameters, exclusions and any special treatment for descriptive statistics.

- All the PK parameters should have at least the following summary statistics: sample size (n), mean, standard deviation (SD), coefficient of variance (CV%), median, minimum, maximum, geometric mean, geometric CV%.

- For in-text tables, Geometric mean (geometric CV%) will be the default method of reporting PK parameters.  $t_{\max}$  should be presented as median, range (minimum, maximum), when presenting the summary statistics.  $t_{1/2}$  should be presented as arithmetic mean, range (minimum, maximum).
- For any parameters that  $n \leq 2$ , SD should not be presented.
- The units for all PK parameters will be provided.
- It is recognized that the number of decimals in reported concentrations, for example: “9632.94401 ng/mL” or “9.963294401 ug/mL” are highly improbable and will be queried (since bioanalytical assays generally do not have this level of precision). Usually the first-in-human dose escalation trial will provide the numerical range of PK parameters e.g. AUC range from 10 to 10,000 ng.hr/mL and  $C_{\max}$  range from 1 to 1000 ng/mL.

In this scenario, for reporting PK parameters such as AUC and  $C_{\max}$ , the following guidance is provided for rounding:

- If the numerical value is below 100 then one decimal place may be used e.g. 0.1 or 99.9.
- For values ranging from >100, whole numbers should be used e.g. 100 or 9999.
- If > 10,000 the clinical pharmacologist may decide on changing units e.g. from  $\mu\text{g/ml}$  to mg/ml.
- For reporting times e.g. for  $t_{\max}$  or  $t_{1/2}$ , if <1 hr use 2 decimals; time up to 24 hr should be reported to one decimal place e.g. 23.5 hr, time >24 hr should be rounded to nearest whole number e.g. 105 hr.

#### 6.6.5. Software

For the calculations of PK parameters Phoenix® WinNonlin® Version 7.0 or higher (Certara, NJ, USA) will be used.

### 6.7. Immunogenicity Analyses

The scope of anti-drug antibodies (ADA) calculations used for characterizing clinical immunogenicity depend on the incidence and kinetics of detected (ADA). Therefore, not all parameters described below may be derived.

The immunogenicity results will be summarized using descriptive statistics by the number and percentage of subjects who develop detectable ADAs. The incidence of positive and neutralizing ADAs will be reported for ADA-evaluable subjects according to the following definitions:

- ADA-evaluable subject: Number of subjects with reportable non-missing baseline result and at least one reportable sample taken after drug administration during the treatment or follow-up observation period with reportable result (used for computing treatment-induced ADA incidence).
- Treatment-emergent ADA: The sum of both treatment-boosted and treatment-induced ADA-positive subjects. Synonymous with “ADA Incidence”.

- Treatment-induced ADA: ADA-evaluable subjects that were ADA-negative at baseline and ADA-positive following administration of biologic product.
- Treatment-boosted ADA: Baseline-positive ADA-evaluable subject with significant increases (4-fold or higher) in ADA titer after biologic drug administration. Baseline-positive ADA-evaluable subject is an ADA-evaluable subject with positive ADA result.
- Persistent ADA: Treatment-induced ADA detected at two or more sampling time points during the treatment (including follow-up period if any), where the first and last ADA-positive samples (irrespective of any negative samples in between) are separated by a period of 16 weeks or longer.
- Transient ADA: Treatment-induced ADA detected only at one sampling time point during the treatment or follow-up observation period, or two or more time points during the treatment, where the first and last ADA-positive samples are separated by a period of less than 16 weeks, and the subject last sampling time point is ADA-negative.
- Neutralizing ADA: patients with positive NAb.

The immunogenicity results will also be listed.

Additional ADA analyses (such as the effect of immunogenicity on PK, and safety) may be conducted if deemed necessary and will be described in a separate analysis plan.

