## 6. STATISTICAL METHODS

### 6.1. Analysis Sets

The Safety Analysis Set will include all the subjects who received either study drug. The Safety Analysis Set is used for all safety analyses.

The PK Analysis Set will include all the subjects who received either study drug and had any measurable concentration of study drug(s). The PK Analysis Set will be used for PK analyses.

The ADA Analysis Set include all the subjects who received either study drug and for whom both baseline ADA and at least 1 postbaseline ADA results are available. The ADA Analysis Set is used for immunogenicity analyses.

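### SAP 6.7 computes treatment-induced ADA incidence over all ADA-evaluable subjects, although baseline-positive subjects cannot be treatment-induced

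*SAP*

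**What the plan says.** Section 6.7 of the SAP sets the reporting population first: "The incidence of positive and neutralizing ADAs will be reported for ADA-evaluable subjects according to the following definitions". The definitions that matter here are these.

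- **Evaluable:** "ADA-evaluable subject: Number of subjects with reportable non-missing baseline result and at least one reportable sample taken after drug administration". The baseline result must exist, but it may be positive or negative. A parenthesis adds that the group is "used for computing treatment-induced ADA incidence".
- **Treatment-induced:** "ADA-evaluable subjects that were ADA-negative at baseline and ADA-positive following administration of biologic product".
- **Treatment-boosted:** a baseline-positive evaluable subject whose titre rises at least 4-fold. The SAP explains that group as follows: "Baseline-positive ADA-evaluable subject is an ADA-evaluable subject with positive ADA result". The words that would tie the positive result to baseline are missing, but the term itself implies them.
- **Treatment-emergent:** "The sum of both treatment-boosted and treatment-induced ADA-positive subjects". The SAP treats this as the same thing as ADA incidence.

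The ADA Analysis Set in SAP 6.1 covers dosed subjects "for whom both baseline ADA and at least 1 postbaseline ADA results are available", again with no condition on what the baseline result was. Protocol section 10.5 refers only to evaluable subjects and names no other denominator.

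**The concern.** The group named for the induced rate contains subjects who are not at risk of the outcome. A subject with detectable ADA before dosing can be counted as boosted but, by the SAP's own definition, never as induced. All evaluable subjects is the natural base for the treatment-emergent total, because subjects of either baseline status can contribute to it. The parenthesis attaches that base to the induced component instead.

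Immunogenicity of each antibody is a secondary objective and endpoint, and counts with percentages are the planned summary. The SAP provides for baseline positivity by giving it a titre rule, and the eligibility criteria in Protocol 4.1 and 4.2 do not exclude pre-existing ADA. Section 6.7 does not ask for the number of baseline-positive subjects to be tabulated. A reader of the summary table alone might therefore be unable to convert the printed rate into the rate among subjects at risk.

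**Working it through.** The plan states no ADA rate and no expected baseline-positive rate, so there is no figure of its own to reproduce.

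**Inputs.** SAP Table 1 and section 5 plan 6 active subjects per cohort. That gives 6 on the combination, 6 + 6 = 12 on BGB-DXP604 alone, and 12 + 6 = 18 on BGB-DXP604 overall. Let n be the evaluable subjects in a reported group, b the baseline-positive subjects among them, and k the treatment-induced subjects. The values of b and k below are assumed.

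**Size of the gap.**

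- Rate as the SAP has it: k/n.
- Rate among subjects at risk: k/(n-b).
- Ratio of the first to the second: (n-b)/n.

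| n | b | k | k/n | k/(n-b) | (n-b)/n |
|---|---|---|---|---|---|
| 6 | 1 | 1 | 1/6 = 16.7% | 1/5 = 20.0% | 0.833 |
| 6 | 1 | 2 | 2/6 = 33.3% | 2/5 = 40.0% | 0.833 |
| 6 | 2 | 1 | 1/6 = 16.7% | 1/4 = 25.0% | 0.667 |
| 12 | 1 | 1 | 1/12 = 8.3% | 1/11 = 9.1% | 0.917 |
| 18 | 1 | 1 | 1/18 = 5.6% | 1/17 = 5.9% | 0.944 |

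If b = 0 the denominators coincide. If k = 0 both rates are zero. In either case nothing changes.

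**How often b is at least 1.** For an assumed baseline-positive probability q and independent subjects, the chance is 1-(1-q)^n.

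| q (assumed) | n = 6 | n = 18 |
|---|---|---|
| 2% | 11% | 30% |
| 5% | 26% | 60% |
| 10% | 47% | 85% |

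**How often the rate changes.** An induced subject must also fall in the same group. Let r be the assumed chance that a baseline-negative subject is induced. The chance that a group has at least one subject of each kind is

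1 - (1-q)^n - [1-(1-q)r]^n + [(1-q)(1-r)]^n.

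For n = 6:

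- q = r = 2%: 1 - 0.886 - 0.888 + 0.785 = about 1%.
- q = r = 5%: 1 - 0.735 - 0.747 + 0.540 = about 6%.
- q = r = 10%: 1 - 0.531 - 0.568 + 0.282 = about 18%.
- q = 5%, r = 20%: 1 - 0.735 - 0.282 + 0.193 = about 18%.

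**The case against.** A reader might infer that the plan's induced rate is biased low as a matter of course. The documents do not support that. The two rates differ only when the same group holds both a baseline-positive and an induced subject, and no baseline-positive rate is given. Moreover, k/n is a correct share of all evaluable subjects. It understates something only if the target is risk among baseline-negative subjects, and the SAP does not name a target.

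A reader might also infer that every ADA rate is affected, or that boosted ADA has no denominator. Neither holds. The treatment-emergent total is unaffected, and the sentence introducing the definitions gives boosted ADA an implied base of all evaluable subjects.

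A third inference is that two cohorts of 6 with equal induction could look different because of the denominator. That is arithmetically possible. If half of the baseline-negative subjects are induced in each, a cohort with no baseline-positive subject shows 3/6 = 50% and a cohort with two shows 2/6 = 33%. But neither SAP 6.7 nor Protocol 10.5 says that ADA is summarised by cohort; the secondary objectives separate BGB-DXP604 alone from the combination. Sampling noise is also far larger than the shift: the exact 95% interval runs from 0.4% to 64% for 1/6 and from 0.5% to 72% for 1/5.

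Finally, the study is descriptive, no decision rule uses an ADA rate, individual results are listed, and the SAP allows that some of these parameters may not be derived. All of this limits the consequences. None of it removes the mismatch: neither document supplies a baseline-negative denominator for the induced rate.

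**Conclusion.** The point holds as a minor mismatch between a stated denominator and the definition of the outcome that it serves. Where a reported group contains at least one baseline-positive and at least one induced subject, the printed induced rate is lower than the rate among subjects at risk by the factor (n-b)/n. With one subject of each kind the gap is 3.3 percentage points at n=6, 0.8 at n=12 and 0.3 at n=18; it is zero if either kind is absent. It grows with more baseline-positive or more induced subjects.

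The sizes rest on assumed counts and on full evaluability of the planned active subjects. The probabilities rest on assumed rates and independence between subjects. The chances for a group of 6 and for 18 subjects answer different questions, and the figures for 18 should not be paired with the gap at n=6. The study's conclusions on safety and PK do not depend on this rate.

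**What to change.** In SAP 6.7, state the following separately for anti-BGB-DXP604 and anti-BGB-DXP593 antibodies:

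- treatment-induced ADA: denominator is baseline-negative ADA-evaluable subjects;
- treatment-boosted ADA: denominator is baseline-positive ADA-evaluable subjects, with the missing reference to baseline added to that definition;
- treatment-emergent ADA: denominator is all ADA-evaluable subjects.

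Print each denominator in the table, and move or reword the parenthesis that now ties all evaluable subjects to the induced rate.

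The change is a short SAP edit and needs no new data. It has two costs. The induced and boosted percentages will no longer add up to the treatment-emergent percentage, although the counts still will, so a table footnote is advisable. The induced rate may also look slightly less favourable.

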The planned cohorts and number of subjects in each cohort are provided in [Table 3](#). Up to 30 subjects (including possible replacement) will be enrolled in the study, which will be conducted in 1 to 2 centers in Australia.

Subjects are expected to be available for follow-up visits until Day 113 of the study. Subjects will be replaced if they cannot complete the infusion or they do not receive any study drug after randomization. Subjects may be replaced if they discontinue from the study before Day 29.

Table 3: Planned Cohorts and Number of Subjects in Each Cohort

Part	Cohort	Number of Subjects in Each Cohort	
		Active Arm	Control Arm (Normal Saline)
1: BGB-DXP604 alone	1A: 10 mg/kg	6	2
	1B: 30 mg/kg ^a	6	2
2: BGB-DXP604 + BGB-DXP593	2A: 30 mg/kg ^b BGB-DXP604 + 30 mg/kg ^b BGB-DXP593	6	2

Abbreviation: SMC, Safety Monitoring Committee.

^a The dose level of BGB-DXP604 in Cohort 1B may be adjusted based on SMC recommendation.

^b The doses of BGB-DXP604 and BGB-DXP593 in Cohort 2A will be recommended by SMC and not exceed 30 mg/kg for each study drug.

Study Assessments

Subjects will be monitored throughout the study for safety, tolerability, PK, and immunogenicity of BGB-DXP604 and BGB-DXP593.

Assessments of safety will include adverse events (AEs), SAEs, clinical laboratory tests, physical examinations, vital signs, and ECGs. An SMC will periodically monitor safety data.

AEs will be graded for severity per the current version of the National Cancer Institute-Common Terminology Criteria for Adverse Events version 5.0 (NCI-CTCAE v5.0). Refer to Section 9 for additional and specific information regarding AE monitoring and reporting.

PK and ADA sampling will be collected at specific intervals from Day 1 to Day 113 ([Appendix 2](#) and [Appendix 3](#)).

Study procedures and assessments are further detailed in Section 7 and Section 8, respectively, and the Schedule of Assessments can be found in [Appendix 1](#). Specific details regarding dose escalation are described in the following sections.

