APPENDIX 3. PHARMACOKINETIC AND ANTIDRUG ANTIBODY BLOOD SAMPLING)

APPENDIX 3A. PHARMACOKINETIC AND ANTIDRUG ANTIBODY BLOOD SAMPLING (Part 1)

Study Day	D1			D2	D3	D4	D5	D8	D15	D22	D29	D43	D57	D71	D85	D113 /EOS
Hours post infusion	0 (predose)	EOI	6	24	48	72	96	168	336	504	672	1008	1344	1680	2016	2688
Window Period (hours)	-60 min to predose	Within 30 min after EOI	± 2	± 6	± 6	± 6	± 6	± 6	± 24	± 24	± 24	± 48	± 48	± 48	± 48	± 48
PK blood sampling	X	X	X	X	X	X	X	X	X	X	X	X	X	X	X	X
ADA sampling	X								X		X		X		X	X

Abbreviations: ADA, antidrug antibody; D, day; EOI, end of infusion; EOS, End-of-Study; min, minutes; PK, pharmacokinetic.

Note: Sample collection must be from the opposite arm that is used for study drug infusion. Refer to laboratory manual for detailed collection instructions.

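### Persistent ADA needs 16 weeks between positive samples, but scheduled post-dose ADA sampling spans 14 weeks, so none can qualify and most responses still positive at Day 113 are neither persistent nor transient

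*SAP*

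**What the plan says.** SAP 6.7 makes persistent and transient ADA subsets of treatment-induced ADA, which it limits to "ADA-evaluable subjects that were ADA-negative at baseline and ADA-positive following administration of biologic product". Persistent ADA requires positives at two or more time points "where the first and last ADA-positive samples (irrespective of any negative samples in between) are separated by a period of 16 weeks or longer".

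The transient definition has two limbs. The first is "Treatment-induced ADA detected only at one sampling time point during the treatment or follow-up observation period". The second covers two or more positives less than 16 weeks apart, followed by the condition "and the subject last sampling time point is ADA-negative". The punctuation leaves open whether that condition also governs the first limb.

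Protocol 3.1 states that "PK and ADA sampling will be collected at specific intervals from Day 1 to Day 113". Appendices 3A and 3B give the same ADA days for both parts: predose, then Days 15, 29, 57, 85 and 113/EOS. Protocol 8.4 allows ±1 day at Day 15 and ±2 days at Day 113. SAP 6.2.1 takes baseline as the last value before dosing, which for ADA is the predose sample.

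**The concern.** Day 1 to Day 113 is exactly 16 weeks, so the threshold looks as though it fits the study. It does not: the Day 1 sample is the baseline, and for treatment-induced ADA that sample must be negative. The interval that matters starts at Day 15.

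If so, a category is defined that no scheduled pattern can enter, and the responses it was meant to identify, those that last, have no place in the persistent/transient split. Detection of ADA over time is a secondary endpoint for both antibodies (Protocol 2.2.2, SAP 4.2). A reported count of zero persistent responses could be read as evidence that ADA does not last, when it would carry no information. A replacement rule chosen after the ADA results are known would be post hoc.

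**Working it through.** **Inputs.** The time row of Appendix 3A reads "Hours post infusion 0 (predose) EOI 6 24 48 72 96 168 336 504 672 1008 1344 1680 2016 2688", and its ADA row has six marks. Aligned to the columns, these are 0 (predose), 336, 672, 1344, 2016 and 2688 h. Appendix 3B is the same. Threshold: 16 × 7 = 112 days = 2688 h.

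**Schedule reproduced.** Day 15: (15 − 1) × 24 = 336 h. Day 113: (113 − 1) × 24 = 2688 h. Both agree with the appendix.

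**Longest gap between two post-dose ADA samples.**

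| Case | Calculation | Days | Weeks |
|---|---|---|---|
| Nominal | 2688 − 336 = 2352 h | 98 | 14.0 |
| Widest window (Day 14 to Day 115) | 2736 − 312 = 2424 h | 101 | 14.4 |
| Narrowest window (Day 16 to Day 111) | 2640 − 360 = 2280 h | 95 | 13.6 |
| Required | 16 × 7 | 112 | 16.0 |

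The shortfall is 112 − 98 = 14 days nominally and 112 − 101 = 11 days at best. With a last sample on Day 115, the first positive would have to fall by Day 115 − 112 = 3. With a first positive on Day 14, the last would have to fall on or after Day 14 + 112 = 126. No such sample is scheduled.

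**Classifying every pattern.** Five post-dose samples give 2^5 − 1 = 31 patterns with at least one positive. Of these, 2^4 = 16 are positive at Day 113 (one at Day 113 only, 15 with an earlier positive as well) and 2^4 − 1 = 15 are negative at Day 113.

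| Reading of the negative-last-sample condition | Persistent | Transient | Neither |
|---|---|---|---|
| Applies to both limbs | 0 | 15 | 16 |
| Applies to the multi-sample limb only | 0 | 15 + 1 = 16 | 15 |

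A subject positive at all five post-dose samples is unclassified on both readings. The two differ only on the subject positive at Day 113 alone: unclassified on the first, transient on the second.

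**A further wording problem.** The multi-sample limb of the transient definition refers to the treatment period alone. Protocol 7.6 starts follow-up the day after infusion, so every post-dose ADA sample lies in follow-up. Read literally, the 15 − 4 = 11 patterns with two or more positives and a negative Day 113 sample would also be unclassified (the 4 are single positives at Days 15, 29, 57 or 85). The persistent definition does include follow-up, so this looks like a drafting slip.

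**The case against.** The arithmetic is hard to dispute; the case against is about how much it matters, and much of it stands.

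- Persistence appears in no objective or endpoint. Protocol 10.5 promises the number and percentage with detectable ADA and the incidence of positive and neutralizing ADA, none of which uses the 16-week rule. This stands: incidence is untouched.
- A reader might infer that the report is bound to show zero persistent ADA. The documents do not go that far. SAP 6.7 warns that some ADA parameters may not be derived, so the line could be left out. But that caveat turns on ADA incidence and kinetics, does not address the schedule, and leaves sustained responses without a summary.
- A reader might infer that these subjects disappear, or that they are the strongest responders. Neither is supported. They remain in the treatment-induced and treatment-emergent counts and in the listings, neither document specifies a persistence table, and the patterns concern duration, not titre.
- The counts out of 31 might be read as the share of subjects affected. They are logical possibilities, not probabilities. The documents give no human ADA rate, and Protocol 1.5 considers immunogenicity low, so the number affected could be zero.
- Sampling times may be changed for later cohorts (Protocol 3.2.2 and 3.3), and unscheduled visits are allowed (Protocol 8.5). No planned change reaches 16 weeks. Early discontinuation brings the EOS sample forward and only shortens the span.

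**Conclusion.** The definition is wrong as written and should be corrected. From scheduled samples taken within their windows, the count of persistent ADA can only be 0, and 15 or 16 of the 31 possible positive patterns, all positive at Day 113, are neither persistent nor transient.

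The reach is limited to a descriptive secondary summary of immunogenicity. Overall ADA incidence, the listings and the primary endpoint are unaffected. How many subjects would be misdescribed cannot be said from the documents; with 3 × 6 = 18 planned active subjects it could be none. One such subject would be 1/6, about 17%, of a cohort's active arm.

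The conclusion assumes that the ADA days in Appendices 3A and 3B are followed and that no ADA sample is added by Day 3 or taken on or after Day 126.

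**What to change.** Before database lock, replace the persistent and transient definitions in SAP 6.7 with rules that the schedule can meet and that place every treatment-induced subject in one category. For example:

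- **Persistent:** positive at two or more post-dose time points including the subject's last sample, or with first and last positives separated by a prespecified interval that the schedule can reach.
- **Transient:** all other treatment-induced ADA with a negative last sample.
- **Indeterminate:** positive at the last sample only.

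The sponsor should choose and justify the interval; 8 weeks is one option, and it has no source in the documents. Apply it to nominal visits. Day 29 to Day 85 is exactly 56 days, and the windows (±1 and ±2 days) make it 53 to 59, so actual dates could change a subject's category. A 14-week cut-off has the same weakness: it equals the nominal Day 15 to Day 113 gap, which can be 95 to 101 days. State also how an early EOS sample is assigned, since the appendices label that column D113/EOS.

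Check with 8 nominal weeks. Persistent takes the 15 patterns positive at Day 113 and earlier, plus 6 negative at Day 113 (4 running from Day 15 to Day 85 and 2 from Day 29 to Day 85), making 21. Transient takes 15 − 6 = 9 and indeterminate 1. The sum is 21 + 9 + 1 = 31.

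Wherever a definition names the observation period, it should include follow-up. The cost is SAP wording and one programming rule, with no new samples.

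### SAP 6.7 can label a subject transient when the only ADA-positive sample is the last one taken; read the other way, it gives that subject no category

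*SAP*

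**What the plan says.** SAP 6.7 starts from treatment-induced ADA, meaning "ADA-evaluable subjects that were ADA-negative at baseline and ADA-positive following administration of biologic product", and sorts these subjects by duration.

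- **Transient, route 1:** "Transient ADA: Treatment-induced ADA detected only at one sampling time point during the treatment or follow-up observation period".
- **Transient, route 2:** at least two positives whose first and last fall under 16 weeks apart. The sentence then closes with one further condition: "and the subject last sampling time point is ADA-negative".
- **Persistent:** "Persistent ADA: Treatment-induced ADA detected at two or more sampling time points during the treatment (including follow-up period if any"), with first and last positives that "are separated by a period of 16 weeks or longer".

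The sampling days are in Protocol Appendix 3A for Part 1, with the same days in Appendix 3B for Part 2. Read against the column headings, the ADA row ("ADA sampling X X X X X X") marks predose, Day 15, Day 29, Day 57, Day 85 and Day 113/EOS. Protocol 7.6.2 makes Day 113 the end-of-study visit for completers, so no planned ADA sample follows it.

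SAP 6.7 also says that some of these parameters may not be derived, depending on the incidence and kinetics of the ADA found, and that immunogenicity results will be listed.

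**The concern.** Calling a response transient tells the reader that it went away. Evidence for that is a negative sample after the positive one. Route 2 asks for this evidence and route 1, as written, does not. A subject who is negative through Day 85 and positive on Day 113 was positive when last seen, yet meets route 1. So does a subject who leaves early and whose only positive is the exit sample.

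Immunogenicity is a secondary objective, and the endpoint is ADA detection over time. Each active arm has 6 subjects, so one wrongly labelled subject is 1/6 = 17% of an arm in whatever table reports duration. The sentence can also be coded in two ways, and the SAP does not say which is intended.

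**Working it through.** The plan states no figure on this point. The check applies the SAP definitions to every possible result pattern on the planned schedule.

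**Inputs**
- Post-dose ADA samples: Days 15, 29, 57, 85 and 113 (Protocol Appendices 3A and 3B). As a check on the column reading, (day − 1) × 24 gives 336, 672, 1344, 2016 and 2688 hours, which matches the hours row.
- Visit windows: ±1 day at Days 15 and 29; ±2 days at Days 57, 85 and 113 (Protocol 8.4).
- Persistent threshold: 16 weeks = 112 days (SAP 6.7).
- Subject: ADA-negative at baseline, all five samples obtained.
- Route 2 speaks only of the treatment period. This is a single-dose study whose post-dose ADA samples all fall in follow-up, so route 2 is taken to include follow-up, as the persistent definition does.

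**Step 1: can persistent be met?** The longest nominal gap is 113 − 15 = 98 days (14.0 weeks). At the window limits it is 115 − 14 = 101 days (14.4 weeks). Both are below 112, so no planned pattern is persistent and every positive pattern meets the under-16-weeks part of route 2.

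**Step 2: count the patterns.** Five samples give 2^5 = 32 patterns, of which 31 have at least one positive.
- Last sample negative with some earlier positive: 2^4 − 1 = 15.
- Last sample positive: 2^4 = 16. One of these is Day 113 only; the other 15 have two or more positives.

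**Step 3: classify.** Reading A attaches the negative-last-sample condition to route 2 only. Reading B attaches it to both routes.

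| Category | Reading A | Reading B | After the fix |
|---|---|---|---|
| Transient | 16 | 15 | 15 |
| Persistent | 0 | 0 | 0 |
| Positive at last sample, duration indeterminate | not defined | not defined | 16 |
| No category | 15 | 16 | 0 |
| Total | 31 | 31 | 31 |

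The readings differ in one pattern, Day 113 only: transient under A, no category under B. Days 85 and 113 together have no category under either. So under A an unresolved last sample bars two positives from transient but not one.

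**Step 4: size.** These counts are of patterns, not probabilities. The documents give no ADA incidence or timing, so what follows is assumption.
- Share of seroconverters first positive on Day 113: equal likelihood across visits gives 1/5 = 20%. If Day 113 has half the weight of each other visit, it is 0.5/4.5 = 11%; with twice the weight, 2/6 = 33%.
- Planned active subjects: 3 × 6 = 18. With 5% to 20% treatment-induced incidence, 18 × 0.05 = 0.9 to 18 × 0.20 = 3.6 seroconverters.
- At the 20% share, 0.9 × 0.2 = 0.18 to 3.6 × 0.2 = 0.72 subjects in the whole trial.

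**The case against.** The best defence is the sentence itself. A comma precedes the closing condition, so it can be read as governing both routes. A subject positive only on Day 113 is then left uncategorised, which is incomplete but not falsely reassuring. The consequence is also small. The study is descriptive, the protocol expects low immunogenicity (Protocol 1.5), the transient category may never be tabulated, and with so few subjects the listings will show when each positive occurred.

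The points about size stand. The grammatical defence stands only in part. The condition is joined to a clause about first and last positives, which fits two or more samples, so the narrower reading is the natural one; nothing else in either document settles it. The broader reading still leaves the subject unplaced, because persistent needs at least two positives.

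A reader might go further and infer that new positives are most likely on Day 113, because circulating drug is lowest then. The human parameters in Protocol Table 1 do project a large fall: at 10 mg/kg and an assumed 70 kg, from about 68 µg/mL on Day 15 to 1.9 µg/mL on Day 113. But the inference needs the drug tolerance of the ADA assay, which the documents do not give; Protocol 8.3 says only that the screening and confirmatory assays are validated. It also ignores when ADA responses arise after a single dose. The point does not need it.

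**Conclusion.** The definition needs correcting. On its ordinary reading it labels a positive last sample as transient when that sample is the only positive; on the other reading it has no place for that subject. This rests on the SAP wording and the sampling schedule alone, not on any assumption about incidence.

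The reach is narrow. A reader might infer that ADA incidence is misreported, but it is not: treatment-induced, treatment-emergent and neutralizing ADA counts do not use the transient rule, and the listings are unaffected. The error sits in one table row, if that row is produced, and under the assumptions above it would be expected to touch fewer than one subject in the trial.

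That persistent cannot be reached on the planned days is a separate matter. Changing the 16-week threshold alone would not place a subject with a single positive on Day 113. It does mean that a repair must also cover subjects with two or more positives whose last sample is positive, since they too have no category now.

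**What to change.** Amend SAP 6.7 in two places.

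1. State that the negative-last-sample condition applies to both routes of transient. For example: *treatment-induced ADA at one or more sampling time points, follow-up included, with first and last positives less than 16 weeks apart and the subject's last sample negative*. This also removes the mismatch in route 2, which mentions the treatment period but not follow-up.
2. Add a category, reported by treatment group: *positive at last sample, duration indeterminate*. It takes every treatment-induced subject whose last sample is positive and who does not meet persistent, whether the subject has one positive or several, and whether the last sample is Day 113 or an early exit visit.

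The cost is one sentence and one table row. No new samples are needed, and no protocol amendment is needed because Protocol 10.5 does not define transient or persistent. The transient count may fall.
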